10.4.4 Changes in Vaginal Flora and Biomarkers

Changes in Nugent scores will be assessed by comparing the Nugent score at enrollment with the one observed at 12 weeks. An abnormal Nugent score is defined as a Nugent score higher than 3 while a normal Nugent score is defined as a score of 3 or less. The proportion of changes between enrollment and week 12 from normal to abnormal will be compared as well as the one from abnormal to normal.

Changes in Nugent score over time are naturally occurring. Based on a sample of 1016 women,⁶⁶ 28.4% of women with a normal Nugent score at enrollment had an abnormal Nugent score 4 months later while 32.8% of women with an abnormal Nugent score at enrollment had a normal Nugent score 4 months later. Therefore, for the purpose of power calculations, we are estimating the proportion of changes in Nugent scores from enrollment to week 12 at 30% in the no IVR arm and this for both from normal to abnormal and from abnormal to normal. Furthermore, we are estimating that 55% and 45% of women will be normal and abnormal, respectively, at enrollment.

The proportion of women with a change in Nugent score from normal to abnormal, at enrollment and 12 weeks, respectively, will be compared between the study IVR and no IVR arms. Assuming that the true proportion of changes in the no IVR arm is 30%, a sample size of 252 women (138 normal women at enrollment and available for the analysis) with a 2:1 randomization will allow detection of an absolute difference of 25% with 80% power (i.e. 30% of women in the no IVR arm and 55% of women in the study IVR arm).

Similarly, the proportion of women with a change in Nugent score from abnormal to normal, at enrollment and 12 weeks, respectively, will be compared between the study IVR and no IVR arms. Assuming that the true proportion of changes in the no IVR arm is 30%, a sample size of 252 women (114 abnormal women at enrollment and available

for the analysis) with a 2:1 randomization will allow detection of an absolute difference of 28% with 80% power (i.e. 30% of women in the no IVR arm and 58% of women in the study IVR arm).

In addition to looking at shifts in the Nugent score, within arm descriptions, and between arm comparisons, will be done to assess clinically meaningful changes in quantitative measures of vaginal flora (defined by more than ≥ 1 log change in dominant members of the microflora) and to assess differences in the quantitative levels of these microflora between arms during follow-up. Quantitative vaginal cultures and vaginal biomarkers will be assessed only at the US sites and therefore the available sample size for these analyses will be 102 women (68 in the study IVR arm and 34 in the no IVR arm). A sample size of 102 women with a 2:1 randomization will allow detection of a medium effect size of 0.59 with 80% power in comparing quantitative levels between arms.

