Note: RTIs requiring treatment, per site specific treatment guidelines, include BV, vaginal candidiasis, other vaginitis, trichomoniasis, chlamydia (CT), gonorrhea (GC), syphilis, active HSV lesions (HSV-2 seropositive women not excluded except with active lesions), chancroid, pelvic inflammatory disease, genital sores or ulcers, or cervicitis. Otherwise eligible participants diagnosed with RTI and/or UTI during Screening will be offered treatment or a prescription for treatment and may be enrolled after completing treatment and all symptoms have resolved. If treatment is completed and symptoms have resolved within 45 days of obtaining informed consent for Screening, the participant may be enrolled.

5. At Screening or Enrollment, has condition that, in the investigator's opinion, would preclude informed consent, make study participation unsafe, complicate

interpretation of study outcome data, or otherwise interfere with achieving the study objectives

6. Severe pelvic relaxation such that either the vaginal walls or the uterine cervix descend beyond the vaginal introitus with valsalva maneuver
7. Participant report of 3 or more sexual partners in the month prior to Screening

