10.7 Participant Accrual and Retention

Based on previous studies of vaginal products with similar eligibility requirements conducted at these 3 sites (i.e. HPTN 059), the accrual of 252 eligible participants with normal reproductive tracts is expected to require the screening of approximately 380 volunteers. The target for retention will be 95% of enrolled participants over the 16 weeks follow-up period. Therefore, it is anticipated that approximately 252 women will be enrolled in the study. Accrual is anticipated to take approximately 6 months and 10 months at the US and non-US sites, respectively.

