10.8.3 Secondary and Exploratory Analyses

Sexual behavior and vaginal hygiene practice

The behavior measures will be collected via ACASI at the Enrollment Visit, follow-up visits, and at the 16-Week/Study Termination Visit. The sexual behaviors and vaginal hygiene practices include the number of sexual partners in the past 3 months, the number of new partners (not asked at enrollment), frequency of sex in the past 7 days, condom use in the past 7 days, condom use during the last sex act, anal sex in the past month, condom use during anal sex in the past month, and vaginal hygiene practices (list of various items/products inserted) in the past 7 days.

For each of the longitudinal behavioral measures, the mean (or the percentage if binary) in each visit in each arm will be computed and tabulated. The generalized estimation equation (GEE) method will be used to assess the difference of each measure between the two arms, accounting for within-subject correlation.

Acceptability

To assess acceptability of the study IVR, the number and percentage of participants in the study IVR arm experiencing at least one negative report of acceptability, including genitourinary discomfort, ring insertion/removal issues, expulsions, and/or changes in participant and/or partner sexual feeling during follow-up will be presented. This binomial proportion will be used to assess the acceptability of the study IVR along with its corresponding 95% confidence interval.

The above acceptability analysis will be supplemented by presenting the above proportion by site along with its corresponding 95% confidence interval.

Vaginal Flora

In order to assess the effect of the study IVR on the vaginal flora of sexually active, HIV-uninfected women, clinically significant changes in vaginal flora will be evaluated by the Nugent score with shift tables from baseline (Enrollment) to follow-up visits at week 4, 8, 12, and 16 to assess the effect on vaginal flora.

The Nugent score is graded 1 to 10 as follows:

- | | |
|------------------|---------|
| 1. Normal, | 0 to 3 |
| 2. Intermediate, | 4 to 6 |
| 3. BV, | 7 to 10 |

Any shift from normal at baseline to intermediate or BV at a follow-up visit, or intermediate or BV at baseline to normal at a follow-up visit, will be considered a clinically meaningful change in vaginal flora. The proportion of changes within each arm will be reported and will be formally compared using the Fisher exact test (from the

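### The Nugent power statements in 10.4.4 assume no losses and an unsourced 45% abnormal share; with the planned 5% loss and Fisher test, power is about 75–77%, and abnormal-to-normal power has no margin below 45%

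*Protocol*

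**What the plan says.** Section 10.4.4 sets the threshold: "An abnormal Nugent score is defined as a Nugent score higher than 3". Section 10.8.3 bands the score as normal 0–3, intermediate 4–6 and BV 7–10, and its first clinically meaningful change is "Any shift from normal at baseline to intermediate or BV at a follow-up visit". Abnormal therefore means intermediate or BV.

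The enrollment shares are given as an estimate: "Furthermore, we are estimating that 55% and 45% of women will be normal and abnormal, respectively, at enrollment". No source is attached to them. The unpublished sample of 1016 women is cited only for the four-month change rates of 28.4% and 32.8%.

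Each power statement uses a full-enrollment denominator:

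- Normal-to-abnormal: "a sample size of 252 women (138 normal women at enrollment and available for the analysis"), 30% against 55%, 80% power.
- Abnormal-to-normal: "a sample size of 252 women (114 abnormal women at enrollment and available" for the analysis), 30% against 58%, which "with a 2:1 randomization will allow detection of an absolute difference of 28% with 80% power".

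Three other places bear on these inputs. Section 10.7 sets a 95% retention target over 16 weeks and says that "the accrual of 252 eligible participants with normal reproductive tracts is expected to require the screening of approximately 380 volunteers". Exclusion 4d in 5.4 bars a reproductive tract infection requiring treatment at Screening or Enrollment. The note to it says "RTIs requiring treatment, per site specific treatment guidelines, include BV", among others, and admits such women once treatment is complete and symptoms have resolved. Section 10.8.3 names the Fisher exact test for the between-arm comparison of shifts.

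**The concern.** The two denominators add up to the whole trial: 138 + 114 = 252. Nobody is lost by week 12, although 10.7 plans for 5% loss over 16 weeks.

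The 45% also appears to take no account of who may enroll. A Nugent score of 7–10 is BV and counts as abnormal. A rule that keeps out or first treats some women with BV can only push the enrolled abnormal share down from that of an unselected population. The change rates in 10.4.4 hint that 45% is an unselected value: if they held in steady state, the abnormal share would be 28.4/(28.4 + 32.8) = 46%. That is an inference; the protocol does not say so.

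At stake is how the flora comparisons are read. Section 2.7.2 treats documentation of flora changes as part of confirming the ring's safety. If the abnormal group is smaller than 114, a null abnormal-to-normal result could be taken as coming from a comparison with 80% power when it had less. The sensitivity of normal-to-abnormal, the direction that would indicate harm, would be understated.

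**Working it through.** **Inputs.** From 10.4.4: 252 women at 2:1; shares 55% and 45%; 30% changing in the no-IVR arm; 55% (normal-to-abnormal) or 58% (abnormal-to-normal) in the IVR arm; 80% power. From 10.7: 95% retention. From 10.8.3: Fisher exact test. Assumed: two-sided alpha 0.05, since none is stated for this comparison, and losses unrelated to arm and to Nugent score.

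**Denominators.** 0.55 × 252 = 138.6 and 0.45 × 252 = 113.4, matching the stated 138 and 114. At 2:1, IVR to no IVR, these split 92:46 and 76:38.

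**Method.** Exact power is the sum of Bin(x; n₁, 0.30) × Bin(y; n₂, p₂) over all tables (x, y) that the test rejects, where p₂ is the IVR-arm rate. For Fisher, a table is rejected if its two-sided hypergeometric p-value is at most 0.05. For the uncorrected chi-square, it is rejected if |x/n₁ − y/n₂| / √[p̄(1−p̄)(1/n₁+1/n₂)] ≥ 1.96, with p̄ = (x+y)/(n₁+n₂).

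**Step 1: the plan's own figures.**

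| Comparison | IVR : no IVR | Fisher | Chi-square |
|---|---|---|---|
| Abnormal-to-normal, 58% v 30% | 76:38 | 80.4% | 83.0% |
| Normal-to-abnormal, 55% v 30% | 92:46 | 79.7% | 80.1% |

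The stated 80% reproduces, so the arithmetic is sound on its inputs.

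**Step 2: apply 95% retention, shares unchanged.** 0.95 × 114 = 108.3, taken as 108 (72:36). 0.95 × 138 = 131.1, taken as 131 (88:43).

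| Comparison | IVR : no IVR | Fisher | Chi-square |
|---|---|---|---|
| Abnormal-to-normal | 72:36 | 77.4% | 79.6% |
| Normal-to-abnormal | 88:43 | 75.1% | 79.0% |

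The loss costs about 3 and 5 points with Fisher. Fisher power moves in small jumps with the exact split: at 88:44 the second row is 76.5%.

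**Step 3: margin on the abnormal share.** By the pooled normal approximation, 80% power for 58% v 30% at 2:1 needs about 111 abnormal women (37 + 74). That is 111/252 = 44% with no loss, or 111/(0.95 × 252) = 111/239.4 = 46% with 5% loss. There is essentially no slack below 45%.

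**Step 4: lower shares.** The protocol gives no figure for the eligible population, so these shares are assumptions. Retention is 95% and the test is Fisher.

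| Abnormal share | Abnormal women (IVR : no IVR) | Power, abnormal-to-normal | Normal women (IVR : no IVR) | Power, normal-to-abnormal |
|---|---|---|---|---|
| 40% | 96 (64:32) | 69% | 144 (96:48) | 79% |
| 35% | 84 (56:28) | 64% | 156 (104:52) | 84% |
| 30% | 72 (48:24) | 59% | 168 (112:56) | 87% |
| 20% | 48 (32:16) | 38% | 192 (128:64) | 91% |

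By the pooled normal approximation, with 5% loss, the difference detectable with 80% power for abnormal-to-normal rises from about 28.5 points at 45% abnormal to 34.5 at 30% and 41.5 at 20%.

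**The case against.** The strongest defence is that the BV exclusion is not a Nugent exclusion. Exclusion 4d reaches only infections requiring treatment, and re-entry turns on completed treatment and resolved symptoms, not on a normal score. No Nugent score appears among the eligibility criteria. The treatment lines in Tables 4 and 5 refer to symptomatic infections, and the BV wet mount is done only if clinically indicated. During follow-up, 8.3.1 does not make asymptomatic BV a reportable event and 9.2 lets it go untreated. Intermediate scores of 4–6 count as abnormal and nothing excludes them. The phrase in 10.7 about normal reproductive tracts belongs to a screening estimate and says nothing definite about flora.

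This stands, and it limits the point. A reader might infer that eligibility removes most abnormal women, and so that abnormal-to-normal power collapses to 40–60%. The documents do not support that: they give no share for eligible women, and the shares in Step 4 are assumed. What survives is that the rules can only lower the share, the 45% has no stated basis, and the power has no room for a fall. The Gram stain is also scheduled for every woman at Screening, so information on Nugent scores is not confined to symptomatic women.

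A second defence is that the retention effect is trivial. With an uncorrected chi-square it nearly is (79.6% and 79.0%). The plan names Fisher, however, and there the loss is 3 to 5 points: modest, but real.

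Third, flora change is a secondary endpoint whose objective is worded descriptively, and the sample size is justified in 10.4.1 and 10.4.2 by safety and adherence. That is true, and nothing here touches enrollment or the primary analyses. But 10.8.3 commits to a formal comparison, and 10.4.4 puts a power figure on it.

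**Conclusion.** The point holds in a limited form. On the plan's own retention target and named test, power is about 77% (abnormal-to-normal) and 75% (normal-to-abnormal) rather than 80%, assuming two-sided 0.05 and losses spread evenly. This is a fault of inputs, not of calculation.

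The 45% abnormal share is unsourced and is not reconciled with exclusion 4d. Below 45%, abnormal-to-normal power falls quickly while normal-to-abnormal power, the direction of harm, rises. How far the true share lies below 45%, if at all, cannot be read from the protocol. The 80% for abnormal-to-normal is therefore unsupported and probably optimistic; a severe shortfall is not demonstrated.

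**What to change.** In 10.4.4:

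1. Restate both power figures with 95% of women available at week 12, the Fisher exact test and an explicit alpha.
2. Give the basis for 45% abnormal among women who pass exclusion 4d, or revise it.
3. Show power or detectable difference for both directions over a range of abnormal shares, for example 20–45%, as in the Step 4 table.

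The cost is a text revision. No extra participants are needed and no analysis changes. The only drawback is a less favourable stated figure for abnormal-to-normal. Labelling that direction as descriptive is open to the sponsor but is a matter of preference, not part of the correction.

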10.4.5 Sexual Behavior and Vaginal Hygiene Practice

The behavior measures will be collected via ACASI at the Enrollment Visit, follow-up visits, and at the 16-Week/Study Termination Visit. The sexual behaviors and vaginal hygiene practices include the number of sexual partners in the past 3 months, the number of new partners (not asked at enrollment), frequency of sex in the past 7 days, condom use in the past 7 days, condom use during the last sex act, anal sex in the past month, condom use during anal sex in the past month, and vaginal hygiene practices (list of various items/products inserted) in the past 7 days.

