11. Able and willing to abstain from the use of non-study vaginal products and/or practices (other than tampons) including but not limited to spermicides, diaphragms, contraceptive vaginal rings, vaginal antibiotic or antifungal medication, sex toys, lubricants or condoms that contain silicone, menstrual cup and douching, within the 14 days prior to Enrollment through study termination

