6.7.1 Prohibited Products and Devices

Concomitant use of non-study vaginal products or other devices including but not limited to diaphragms, sex toys, douching, intravaginal cleansing practices, female condoms, contraceptive vaginal ring, cervical caps, lubricants or condoms that contain silicone, and/or spermicides are prohibited for the duration of the study except for tampons. Participants who report such use will be counseled regarding the use of alternative methods and provided or referred to family planning services for provision of alternative methods as applicable.

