7.2 Enrollment Visit

Table 5: Enrollment Visit

Enrollment Visit	
Component	Procedures
Administrative and Regulatory	
 • Review/update locator information • Obtain written informed consent for enrollment and storage and future testing of specimens • Confirm eligibility • Provide available test results • Follow procedures for randomization assignment • Schedule next study visit, if applicable • Provide reimbursement for visit

Behavioral		
 • Administer baseline behavioral assessment • Administer baseline acceptability assessment • Provide counseling 
 ○ Contraceptive ○ HIV/STI risk reduction/male condom ○ Protocol adherence ○ For Group A, product use/adherence ○ HIV testing process*
Clinical		
 • Update obstetric history • Update medical/menstrual history • Update concomitant medications • Document pre-existing conditions • Perform targeted physical exam (see Appendix III) • Collect urine sample • Collect blood sample • Perform pelvic exam (see Appendix III) • Perform naked eye examination and colposcopic examination as described by the CONRAD/WHO Manual for the Standardization of Colposcopy for the Evaluation of Vaginal Products (Update 2004) to assess condition of vaginal and/or cervical epithelium or blood vessels. Digital images may be recorded • Collect pelvic samples • Treat or prescribe treatment for symptomatic UTI/RTIs/STIs or refer for other findings*
Laboratory	Urine	
 • Qualitative hCG • Dipstick UA* • Urine culture*
	Blood	
 • Plasma archive • Syphilis serology* • HIV-1 test*
	Pelvic Samples	
 • Gram stained smear of vaginal fluid, obtained from lateral vaginal wall • Vaginal swabs for vaginal flora assessment • Cervical swab for innate factors (US sites only) • Vaginal fluid tested for Trichomonas vaginalis by rapid test (CLIA waived test)* † • Vaginal pH* † • Vaginal fluid for wet mount microscopy (KOH for vulvovaginal candidiasis)* † • Vaginal fluid for wet mount microscopy (saline for BV)* † • Herpes culture †* • Cervical swab for NAAT for GC/CT*

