7.8.2 Acceptability and Behavioral Change

Acceptability will be measured via questions about ease of insertion and removal, feeling the study IVR during daily activities and sex, partner awareness of the study IVR during sex, partner attitude towards the ring, and willingness to use an HIV protective ring in the future, if one were available. Behavioral change potentially related to study IVR use will be assessed via comparisons between sexual activity and vaginal hygiene at enrollment and at follow-up visits, and via comparisons of sexual activity and vaginal hygiene between the study IVR arm and no ring arm.

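### The Enrollment vaginal hygiene answer covers days when women are already meant to abstain, so change from Enrollment cannot be read as change from usual practice

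*Protocol*

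**What the plan says.** A secondary objective (3.2) is to describe changes in vaginal hygiene practices in the ring and no-ring groups over 12 weeks.

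- **Measure.** Section 10.4.5, repeated in 10.8.3, lists "vaginal hygiene practices (list of various items/products inserted) in the past 7 days".
- **Timing.** "The behavior measures will be collected via ACASI at the Enrollment Visit, follow-up visits, and at the 16-Week/Study Termination Visit". Table 5 (7.2) has the entry "Administer baseline behavioral assessment". Table 4 (7.1) and Appendix I show no behavioural assessment at Screening.
- **Eligibility.** Criterion 11 (5.3) reads "Able and willing to abstain from the use of non-study vaginal products and/or practices (other than tampons" and ends its list of examples with "menstrual cup and douching, within the 14 days prior to Enrollment through study termination".
- **On study.** Section 6.7.1 names douching and intravaginal cleansing among the practices that "are prohibited for the duration of the study except for tampons". This applies to both arms, and women who report such use are counselled.
- **Analysis.** Section 7.8.2 says: "Behavioral change potentially related to study IVR use will be assessed via comparisons between sexual activity and vaginal hygiene at enrollment and at follow-up visits". It then adds a second comparison, between the ring arm and the no-ring arm. Section 10.8.3 tabulates each measure by visit and arm and compares the arms by GEE.

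**The concern.** The baseline for hygiene is taken while women are already meant to be abstaining from the practices being measured. A habitual user who stops in order to qualify answers none at Enrollment. If she stays off during the trial, she is recorded as unchanged. If she partly resumes, she is recorded as having started something new.

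At stake is the enrollment-to-follow-up comparison, one of the two that 7.8.2 names. Read as change from habit, it would be too small when practices fall and could point the wrong way. Analysis cannot repair this afterwards, because no measure listed in the protocol records what women did before the abstention.

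**Working it through.** **Windows side by side.** Take Enrollment as day 0. The hygiene item covers days -7 to 0 (10.4.5). The abstention covers days -14 to 0 and continues to termination (criterion 11). The first window lies entirely inside the second. Nothing behavioural is scheduled before day 0.

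**Size of the error.** The protocol gives no hygiene rate, power or sample size for this measure, so there is no stated figure to reproduce. The inputs below are assumptions:

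- p = proportion of women with a habitual practice before the study: 30%, range 10% to 50%
- c = proportion of those women who abstain in the 7 days before Enrollment: 50% to 100%
- r = proportion of those women practising at week 12: 40%

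Reporting is taken as truthful.

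- Enrollment value = p(1 - c)
- Week 12 value = pr
- Change from Enrollment = pr - p(1 - c)
- Change from habit = pr - p
- Error = [pr - p(1 - c)] - [pr - p] = pc

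The error does not depend on r. New uptake by women without the habit would add the same amount to both changes, so it leaves the error as it is.

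With p = 30% and r = 40%, week 12 is 0.30 x 0.40 = 12%, and change from habit is 12 - 30 = -18 points:

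| Compliance c | Enrollment value | Change from Enrollment | Error pc |
|---|---|---|---|
| 100% | 0% | +12 points | 30 points |
| 90% | 3% | +9 points | 27 points |
| 70% | 9% | +3 points | 21 points |
| 50% | 15% | -3 points | 15 points |

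Across c = 50% to 100%, the error is 5 to 10 points at p = 10% and 25 to 50 points at p = 50%.

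**When the sign reverses.** Change from Enrollment is positive when pr > p(1 - c), that is, when c > 1 - r. With r = 40% the threshold is c = 60%. Below it the direction is right, but the fall is still understated by pc.

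**Comparison between arms.** The abstention before Enrollment precedes randomisation, so the expected Enrollment value B is the same in both arms. With follow-up rates F1 (ring) and F0 (no ring), the difference in change is (F1 - B) - (F0 - B) = F1 - F0. The suppressed baseline cancels.

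**The case against.** **The objective is comparative.** It sets the ring group against the no-ring group, and 10.6 gives comparison of changes in hygiene as one reason for the no-ring arm. The only formal test in 10.8.3 is between arms. This stands. A reader might infer that the secondary objective cannot be answered at all, and the protocol does not support that. The arm comparison remains valid for hygiene on study. Its limit is that both arms are under the 6.7.1 prohibition, so it compares departures from a rule and not free behaviour.

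**Change from habit may not be the target.** Section 7.8.2 is about change potentially related to ring use, and a woman who stops douching to qualify changes because of the eligibility rule. An Enrollment value taken under the same restriction as follow-up is a defensible starting point for change after ring insertion. This also stands, and it is why a measure of usual practice should supplement the Enrollment item and not replace it. A baseline from before Screening would mix the effect of entering the trial with any effect of the ring.

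**The baseline need not be zero.** A reader might infer that it is forced to about zero and that the sign of the change is always reversed. Neither follows. Criterion 11 asks for ability and willingness to abstain, and tampons are exempt although they could appear on a list of items inserted. Intravaginal cleansing is named in 6.7.1 but not in the open-ended list of criterion 11. ACASI was chosen partly to reduce socially desirable answers (2.7.2). Universal reversal is a consequence of assuming full compliance; at 50% compliance in the example above it is gone. The error pc remains at any compliance above zero.

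**The questionnaire is not shown.** Section 10.4.5 introduces its list as what the measures include, so a usual-practice question may exist. If so, only the analysis text needs changing. The measures and recall windows that the protocol does list contain none.

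**Conclusion.** The point holds in a limited form. The Enrollment hygiene value is suppressed by the abstention and does not represent usual practice, so the within-woman comparison in 7.8.2 cannot be read as change from habit. It understates any reduction by habitual prevalence times compliance, which is 15 to 30 points at an assumed 30% prevalence and 50% to 100% compliance. It shows an apparent increase once compliance exceeds one minus the proportion practising at follow-up. The overlap of the windows is certain from the text; the percentages are illustrative and rest on assumed prevalence, compliance and resumption.

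The GEE comparison of arms and the sexual behaviour items are unaffected by the suppressed baseline. This is a descriptive secondary objective with no power claim, and the primary objectives are not touched. The change is still worth making, because it is cheap and the missing information cannot be recovered later.

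**What to change.** 1. Ask the same item list once more, at Screening or in the Enrollment ACASI, with a recall frame that predates the abstention, for example usual practice in the month before Screening. Table 4 sets a maximum of 45 days between Screening and Enrollment but no minimum, so part of that month could fall within the 14 days. Asking for usual practice, not a count of recent days, limits this.
2. In 7.8.2 and 10.8.3, report change from usual practice alongside change from Enrollment, and say what each one measures.
3. Use usual practice as a baseline covariate in the hygiene GEE. The arm comparison is valid without it; the covariate takes account of what each woman did before the study.
4. Keep the 7-day Enrollment item as the baseline under restriction and as a check on criterion 11.
5. Label follow-up hygiene reports as practice under a study prohibition.

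The cost is a slightly longer questionnaire, a longer recall period for one item, and short additions to 7.8.2 and 10.8.3. If the item is asked at Screening, Table 4 and Appendix I need a matching entry. No extra visit, specimen or participant is needed.
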